3.14.1.3 Primary Efficacy Sensitivity and Supplementary Analysis

The following sensitivity and supplementary analyses will be performed for the primary efficacy endpoints.

- ***Analysis by iTD:*** The primary efficacy endpoint analysis will be performed on each iTD subgroup.
- ***Imputation of Missing Data:*** Multiple imputation will be used to impute missing blood Phe data during the DEP. The imputation of missing data analysis will assume the data is missing at random (MAR). The methodology for the multiple imputation is provided in [Section 3.18.1](#). As discussed in [Section 3.14.1.1](#), the imputation will not utilize the data from the DEP Weekly substudy. The analysis model will be the same model as the DEP primary efficacy endpoint analysis. The DEP FAS will be the primary efficacy analysis population for this analysis.
- ***Analysis of Covariance:*** The primary efficacy endpoint will be analyzed using an analysis of covariance (ANCOVA) model. The percent change from DEP baseline in blood Phe level at the last

measurement of the iTD of SYNB1934v1 will be the dependent variable is a factor and DEP baseline Phe is a covariate. For this analysis the 2 Phe assessments occurring at the last measurement of the iTD of SYNB1934v1 will be averaged (i.e., if just 1 Phe assessment at this timepoint, that value will be used).

Least-squares means for the percent change from baseline overall dose level, along with the corresponding █ confidence intervals and p-values testing a percent change from baseline equal to 0, will be calculated.

This will be an observed-case analysis using the DEP FAS population, missing data will not be imputed.

- ***Excluding Participants on a Dropped Dose:*** The primary efficacy endpoint analysis will be performed on the DEP FAS using an observed case analysis which excludes participants who were.
- ***Excluding Observations after Treatment Discontinuation, Antibiotic use, or Prohibited Medication:*** The primary efficacy endpoint analysis will be performed on the DEP FAS using an observed case analysis which excludes observations after the following intercurrent events occur in the DEP: Treatment discontinuation, antibiotic use, prohibited medication use.
- ***RWP PPS Analysis:*** The primary efficacy endpoint analysis will be performed using the responder DEP PPS analysis set (defined in [Section 3.5](#)).
- ***MMRM Analysis by Dose Level:*** The percent change in blood Phe level will be analyzed using an MMRM model. All available Week 3 blood Phe data will be used. The model will have percent change from baseline as the dependent variable. Dose level (as a categorical variable) and baseline blood Phe will be fixed effects. The MMRM analysis will be based on the restricted maximum likelihood method. A Kenward-Roger approximation will be used for the denominator degrees of freedom. The covariance structure for the repeated-measures will be a direct product of unstructured for the multiple Week 3 visits (i.e., a total of 5 possible Week 3 visits, 3 for each dose level and 2 for possible repeats of the 3×10^{11} and 6×10^{11} doses) and compound symmetry for the repeated assessments at a particular visit. As such the covariance structure will use the direct product structure “UN@CS” as defined in SAS PROC Mixed.

This will be an observed-case analysis, this analysis will be performed using the DEP FAS and also using the responder RWP FAS population, missing data will not be imputed.

If the MMRM analysis does not converge, the repeated measures at each blood Phe assessment will be averaged together and the average of the repeated measures will be used to calculate the percent change in blood Phe level, the dependent variable. The model will have percent change from baseline as the dependent variable (i.e., using the averaged value at Week 3 visit). The MMRM model will be the same (i.e., same set of fixed effects) with the exception that the covariance structure for the repeated-measures will be unstructured for the multiple Week 3 visits (i.e., a total of

5 possible Week 3 visits, 3 for each dose level). If this model does not converge a compound symmetry covariance structure will be used.

Additionally, histograms illustrating the DEP Week 3 change and percent change from baseline in blood Phe by treatment group will be produced, overall and by iTD.

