The responder RWP PPS is defined as all responder RWP FAS participants, who had no major protocol deviations that would affect efficacy, had at least 75% treatment compliance, whose dietary Phe remained within 20% of their DEP baseline value, and who did not require systemic antibiotic treatment during DEP or RWP. The responder RWP PPS will be used as a sensitivity analysis for the RWP primary efficacy endpoint. Major protocol deviations will be determined prior to the RWP database lock. Analyses on the responder RWP PPS will be performed according to the randomized treatment group.

Sample Size Considerations:

[REDACTED]. This assumes a dropout rate of 10% in the DEP and approximately 50% of participants are responders. If, during the course of the study, it becomes apparent that the assumptions were not accurate or a dose level is dropped after the interim analysis, the number of participants enrolled into the DEP may be adjusted. The study has over 98% power in testing that the mean percent change from baseline at the last measurement of the iTD in blood Phe level is different from 0. This assumes a mean percent reduction in blood Phe levels of -11%, a standard deviation of 17%, a 10% drop-out rate, and a 2-sided Type I error rate of 0.05. The mean percent reduction and standard deviation in blood Phe values used in the power calculations are based on results from a similar study in participants with PKU.

A sample size of [REDACTED] in the responder RWP [REDACTED] to detect a difference in the mean change in blood Phe level from baseline to Week 4 between the SYNBI934v1 and placebo treatment groups. This assumes a mean treatment group difference in blood Phe of -245  $\mu\text{mol/L}$  between the SYNBI934v1 and placebo groups, a change from baseline standard deviation of 247  $\mu\text{mol/L}$ , 1:1 randomization of SYNBI934v1 and placebo, a 5% drop-out rate in the RWP, and a 2-sided Type I error rate of 0.05. The power was calculated via a t-test. The mean treatment group difference and standard deviation in blood Phe values used in the power calculations are based on results from a similar study in participants with PKU.

Primary Efficacy Analysis:

*DEP (Part 1):* The DEP primary efficacy endpoint is the percent change from DEP baseline in blood Phe level at the last measurement of the iTD of SYNBI934v1. The last measurement is the participant's last Week 3 blood Phe level at the iTD of SYNBI934v1.

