Per-protocol analysis set (PPS): The DEP PPS is defined as all DEP FAS participants, who had no major protocol deviations that would affect efficacy, completed their final 3-week iTD, whose dietary Phe remained within 20% of their DEP baseline value (see [Section 3.10.2](#)), and who did not require systemic antibiotic treatment during DEP (see [Section 3.12](#)). The DEP PPS will be used as a sensitivity analysis for the DEP primary efficacy endpoint.

The responder RWP PPS is defined as all responder RWP FAS participants, who had no major protocol deviations that would affect efficacy, had at least 75% treatment compliance (see [Section 3.13.1](#)), whose dietary Phe remained within 20% of their DEP baseline value (see [Section 3.10.2](#)), and who did not require systemic antibiotic treatment during DEP or RWP (see [Section 3.12](#)).

The responder RWP PPS will be used as a sensitivity analysis for the RWP primary efficacy endpoint. RWP major protocol deviations will be determined in a blinded manner prior to the RWP database lock. Analyses on the responder RWP PPS will be performed according to the randomized treatment group.

Following the protocol deviations handling plan, major protocol deviations that would affect efficacy will be determined by a review of the functional team members (i.e., the set of functional team members will be defined in the protocol deviations handling plan), which will be blinded for the RWP.

RWP Randomized analysis set: The RWP Randomized analysis set is defined as all participants randomized into the RWP. The responder Randomized analysis set is defined as participants in the Randomized analysis set who are responders. The nonresponder Randomized analysis set is defined as participants in the Randomized analysis set who are nonresponders.

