3.14.1.5 Key Secondary Sensitivity and Supplementary Analysis

- ***Change from baseline in blood Phe level at last measurement of the iTD of SYNB1934v1***

- ***Analysis by iTD:*** The analysis will be performed on each iTD subgroup.
- ***Imputation of Missing Data:*** Multiple imputation will be used to impute missing blood Phe data during the DEP. The imputation of missing data will assume the data is missing at random (MAR). The methodology for the multiple imputation and analysis is provided in [Section 3.18.1](#). The analysis model will be the same model as the DEP key secondary endpoint analysis. This analysis will be performed on the DEP FAS population.
- ***Analysis of Covariance:*** The change from baseline in blood Phe level at last measurement of the iTD of SYNB1934v1 endpoint will be analyzed using an ANCOVA model. The change from DEP baseline in blood Phe level at the last measurement of the iTD of SYNB1934v1 will be the dependent variable, using the average of the duplicate blood Phe levels (i.e., if one of the values is missing, the non-missing value will be used). The ANCOVA has Treatment as a fixed effect and DEP baseline Phe is a covariate. This will be an observed-case analysis using the DEP FAS population, missing data will not be imputed.

- ***Excluding Observations after Treatment Discontinuation, Antibiotic use, or Prohibited Medication:***

Medication: The key secondary efficacy endpoint analysis will be performed on the DEP FAS using an observed case analysis which excludes observations after the following intercurrent events occur in the DEP: Treatment discontinuation, antibiotic use, prohibited medication use.

- ***RWP PPS Analysis:*** The analysis will be performed using the responder RWP PPS analysis set (defined in [Section 3.5](#)).

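### The per-protocol checks of the DEP endpoints are assigned to responder-only sets, one of them undefined, instead of the DEP PPS

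*SAP*

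**What the plan says.** SAP 3.5 defines two per-protocol sets.

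- **DEP PPS.** It is drawn from all DEP FAS participants, without regard to response. Its role is stated: "The DEP PPS will be used as a sensitivity analysis for the DEP primary efficacy endpoint". Protocol 8.2 and the protocol synopsis say the same.
- **Responder RWP PPS.** It is drawn from the responder RWP FAS, with further conditions on RWP compliance and on antibiotic use in the DEP or RWP. Its role is also stated: "The responder RWP PPS will be used as a sensitivity analysis for the RWP primary efficacy endpoint".

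The DEP efficacy sections depart from this in three bullets, each headed as an RWP PPS analysis.

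- SAP 3.14.1.3, DEP primary (percent change at the iTD): "The primary efficacy endpoint analysis will be performed using the responder DEP PPS analysis set", with a pointer to SAP 3.5.
- SAP 3.14.1.5, first key secondary (absolute change at the iTD): "The analysis will be performed using the responder RWP PPS analysis set".
- SAP 3.14.1.5, second key secondary (reduction of at least 20% at any time in the DEP): the same sentence.

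SAP 3.20, which lists changes from the protocol, includes several changes to populations but not this one.

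**The concern.** A per-protocol analysis of the DEP should show whether the DEP FAS result survives removal of participants with major deviations, unstable diet or systemic antibiotics. Restricting it to responders adds a filter on the DEP blood Phe result itself. The estimate then moves toward efficacy for a reason unrelated to protocol adherence, and agreement with the DEP FAS result says little.

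There is also a practical problem. A programmer sent to SAP 3.5 for a responder DEP PPS will not find one. No instruction in SAP 3.14.1 uses the unrestricted DEP PPS, so the analysis promised in SAP 3.5 and protocol 8.2 is missing from the section that should specify it.

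For the key secondaries, the responder RWP PPS also requires RWP dosing, at least 75% compliance and no antibiotics in the RWP. These conditions arise after the DEP measurement.

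**Working it through.** **1. Text comparison**

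| Endpoint | Per-protocol set in SAP 3.5 and protocol 8.2 | Set named in SAP 3.14.1 |
|---|---|---|
| DEP primary | DEP PPS | Responder DEP PPS (not defined) |
| DEP key secondary, absolute change | None named | Responder RWP PPS |
| DEP key secondary, at least 20% reduction | None named | Responder RWP PPS |

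The first row is a direct conflict. The other two are a misapplied set, because nothing assigns a per-protocol set to those endpoints.

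**2. The dichotomous key secondary**

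SAP 2.2 judges response at Week 3 of the iTD; SAP 3.4.3 judges it at any time in the DEP. A responder under either rule has had a reduction of at least 20% at some time in the DEP. The proportion in a responder set is therefore 100%, whatever the drug does.

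**3. Inputs for the change endpoints**

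- Protocol synopsis, Sample Size Considerations: "This assumes a mean percent reduction in blood Phe levels of -11%, a standard deviation of 17" percent, and "approximately 50% of participants are responders".
- Number of visits, from SAP 3.14.1.3: "a total of 5 possible Week 3 visits, 3 for each dose level and 2 for possible repeats".
- My assumptions: normal percent changes and between-visit correlation of 0.3 to 0.7.

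The protocol's figure of over 98% power cannot be reproduced directly because the DEP sample size is redacted. With mean -11%, SD 17% and two-sided 0.05, a one-sample t-test exceeds 98% from 41 evaluable participants, or 41/0.9 = 45.6, so 46 enrolled. That figure is not in dispute.

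**4. Response judged at the last iTD visit**

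Responder mean = μ − 17·φ(z)/Φ(z), with z = (−20 − μ)/17.

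- μ = −11: z = −0.529, φ = 0.3468, Φ = 0.2983. The mean is −11 − 17 × 0.3468/0.2983 = **−30.8%**, with 29.8% responders.
- μ = 0 (no effect): z = −1.176, φ = 0.1997, Φ = 0.1197. The mean is **−28.4%**.
- μ = −20 (50% responders): z = 0. The mean is −20 − 17 × 0.3989/0.5 = **−33.6%**.

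**5. Response judged at any visit**

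Simulated exchangeable visits with mean −11% and SD 17%; a responder has any visit at or below −20%; the outcome is the last visit.

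| Visits | Correlation 0.3 | 0.5 | 0.7 |
|---|---|---|---|
| 2 | −21.6% | −23.4% | −25.5% |
| 3 | −18.4% | −20.7% | −23.4% |
| 4 | −16.8% | −19.2% | −22.1% |
| 5 | −15.7% | −18.2% | −21.3% |

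Responders make up 41% to 71% in these cases. Over steps 4 and 5 the responder mean at μ = −11 is 15.7/11 = 1.4 to 30.8/11 = 2.8 times the true mean. With no drug effect and three visits (correlation 0.3 to 0.8), responders still average −12.9% to −21.5%, and a test against 0 rejects in 88% to 100% of simulated samples of 20.

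**6. Sensitivity to the model**

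- Visit means proportional to dose (protocol 1.6 describes a linear relationship), −11% at the last iTD visit, two or three visits, no de-escalation: −21.5% to −27.8%.
- Two completed levels, a failed third and a return to the second (means −5.5, −11, −11): −19.6% to −24.5%.
- Three paths with de-escalation after a completed higher dose: −12.0% to −20.7%. The mildest value comes from a five-visit path in which 87% to 94% respond, far from the planned 50%.
- Mean reset so that 50% respond, one to five visits: the responder mean is 7.7 to 13.6 points below the overall mean.

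**The case against.** The best reply is that the primary-endpoint bullet is a drafting slip which SAP 3.5 already resolves. Only one DEP PPS exists, its purpose is stated, and nearby bullets have other visible wording faults. The wording closely matches the RWP bullet in SAP 3.14.2.3, which supports a carry-over. That is probably how it arose, but the instruction in the analysis section still names a different population, and the table shells are in a separate document.

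For the key secondaries, one can say that nothing is contradicted and that DEP change among RWP responders is a legitimate supplementary description. The SAP does plan such work in the dose-level MMRM: "this analysis will be performed using the DEP FAS and also using the responder RWP FAS population". There, however, the responder set is run beside the DEP FAS. In the three bullets at issue it is the only per-protocol set. The absolute-change result would answer a different question from the one a per-protocol check asks. The 20% proportion would answer none, although a visible 100% is unlikely to mislead anyone.

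Two points stand in full. The consequence is limited: SAP 2.1 places the primary evidence of efficacy in the RWP comparison, and the DEP primary keeps its multiple-imputation, ANCOVA and intercurrent-event checks on the DEP FAS. And the size of the bias depends on assumed correlations and visit paths, so its range is wide.

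**Conclusion.** The concern holds. The DEP primary per-protocol check is placed on an undefined responder set, against SAP 3.5 and protocol 8.2, and both DEP key secondaries are given a set built for the RWP.

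That the 20% proportion equals 100% needs no assumption. The shift in percent change rests on normality, the protocol's -11% and 17%, and the assumed visit structure. It is about 20 points under the iTD rule and about 5 to 15 points under the any-time rule with two to five equal-mean visits, and it can fall to 1 point on an atypical de-escalation path. The documents give no SD for absolute change in the DEP; the same ratios apply if percent change is independent of baseline. The added selection on RWP dosing, compliance and antibiotics is not quantified.

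This should be corrected, but it threatens no confirmatory result.

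**What to change.** In SAP 3.14.1.3 and in both bullets of SAP 3.14.1.5, change the heading to DEP PPS Analysis and name the DEP PPS of SAP 3.5, with no responder restriction. For the primary endpoint this restores what SAP 3.5 and protocol 8.2 already promise. For the two key secondaries it is a consistent extension, which SAP 3.5 could state in one sentence.

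If a responder summary of the DEP is also wanted, define the set in SAP 3.5 under a single responder rule, label it descriptive with no test against 0, list it in SAP 3.20, and present it in addition to the DEP PPS analysis.

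The essential cost is three wording edits, made before unblinding. The DEP PPS is already defined and no new data are needed.

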2.2 STUDY DESIGN

This is a 3-part, Phase 3 study consisting of a dose-escalating, open-label period (DEP; Part 1) of up to 15 weeks, followed by a 4-week, double-blind, placebo-controlled, randomized withdrawal period (RWP; Part 2), and an open-label extension (OLE; Part 3) of up to 36 months. [Figure 1](#) presents a study schematic.

In the DEP, all enrolled participants will maintain a stable diet reflecting their baseline Phe intake and receive escalating doses of SYNB1934v1 from approximately 3 to 15 weeks to determine an iTD, which is defined as the highest dose the participant is able to tolerate. A participant will be defined as having reached an iTD if they tolerate 3 weeks at a dose, regardless of whether other doses are tolerated.

Blood Phe level will be measured at each dose level after 3 weeks at that level. A responder will be defined as a participant who achieves a $\geq 20\%$ reduction in blood Phe level compared to DEP baseline on their iTD. For inclusion in the RWP primary efficacy analysis population, response will be assessed at the third week of a participant's established iTD for SYNB1934v1.

If at any time during a 3-week dosing interval in the DEP the participant or investigator considers a dose level to be intolerable, the dose may be de-escalated after discussion with the medical monitor. In this case, the participant will restart 3 weeks at the lower level iTD. After de-escalation, participants cannot escalate to a higher dose again during.

[figure not shown]
The DEP will contain an optional substudy (DEP weekly substudy) to evaluate the range and variability of [REDACTED] at each dose level. The [REDACTED] participants in this substudy will have weekly Phe and Tyr value assessments during the DEP (i.e., with Tyr assessments being primarily assessed for safety).

Once the first [REDACTED] participants have attained an iTD and completed the DEP or the [REDACTED] has a baseline DEP and has been in the study for [REDACTED], whichever occurs earlier, the DEP data will be evaluated by an independent Data Monitoring Committee (DMC). The DMC will use a pre-specified set of criteria based on both safety and efficacy to determine whether the dose regimen is appropriate or whether any doses should be discontinued as well as whether the study should be stopped for futility. Enrollment will not be paused during the interim analysis.

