3.4.3 Calculations for the DEP Responder

As discussed in [Section 2.2](#), a responder is defined as a participant who achieves a $\geq 20\%$ reduction in blood Phe level compared to DEP baseline. The following are additional details regarding the definition of a responder:

- A participant will be considered a responder if they met the $\geq 20\%$ reduction in blood Phe level at any time in the DEP.
- This will include the scheduled Week 3 blood Phe assessments at the end of each 3-week dosing period.
- This will not include assessments that were made specific to the participants included in the DEP Weekly substudy ([Section 2.3.2](#)).

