3.5 Analysis Populations

Analysis populations will be defined for each of the 3 parts of the study (DEP, RWP, and OLE).

Full analysis set (FAS): The full analysis sets are based on the intention-to-treat principle. The DEP FAS includes all participants enrolled in the DEP who take at least one dose of DEP study medication.

The RWP FAS is defined as all participants randomized into the RWP who take at least one dose of RWP study medication. Additionally:

- The responder RWP FAS is defined as participants in the RWP FAS who are responders
- The nonresponder RWP FAS is defined as participants in the RWP FAS who are nonresponders.

A responder is defined as a participant who achieves a $\geq 20\%$ reduction in blood Phe level compared to DEP baseline on SYNB1934v1.

The responder RWP FAS will be the primary efficacy analysis population for the RWP. Analyses on the RWP FAS will be performed according to the randomized treatment group.

In the event that, based on the interim analysis results utilizing the criteria provided in [Table 10](#), the DMC recommends dropping either the 1×10^{12} or the 1×10^{12} and 6×10^{11} doses the following will occur:

- The participants in the DEP who have an iTD corresponding to a dropped dose will go directly into the OLE part of the study (i.e., as opposed to being randomized into the RWP).
- The RWP FAS, responder RWP FAS, and nonresponder RWP FAS, will exclude all participants whose iTD dose level was dropped.

These participants who are excluded from the RWP FAS will be summarized separately.

Safety analysis set (SAS): For each of the 3 study parts, the SAS will include all participants who received any amount of IMP in the corresponding study part with treatment assignment based on the treatment received.

For the RWP the safety analyses will be presented for the RWP SAS overall as well as by responder/nonresponder subgroups. Similarly, the OLE safety analyses will be presented for the OLE SAS overall as well as by responder/nonresponder subgroups.

A participant will be considered receiving treatment if the eCRF question “did the patient receive any study drug doses” is answered “Yes” and there is a corresponding non-missing date.

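### The supplementary DEP by-dose MMRM is also run in the responder RWP FAS, a set selected on the outcome being modelled, so its least-squares means are biased toward benefit

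*SAP*

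**What the plan says.** SAP 3.14.1.3 opens its list with "The following sensitivity and supplementary analyses will be performed for the primary efficacy endpoints". One item is the MMRM Analysis by Dose Level for percent change from DEP baseline. Of the data it says "All available Week 3 blood Phe data will be used"; of the model, "Dose level (as a categorical variable) and baseline blood Phe will be fixed effects". Estimation is REML with Kenward-Roger degrees of freedom. On the population it says "this analysis will be performed using the DEP FAS and also using the responder RWP FAS population". SAP 3.14.1.5 repeats the analysis, with the same two populations, for absolute change.

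SAP 3.5 states: "The responder RWP FAS is defined as participants in the RWP FAS who are responders". A responder has a fall of at least 20% from DEP baseline. The SAP gives two rules for when that fall is judged:

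- **iTD rule.** SAP 2.2: "For inclusion in the RWP primary efficacy analysis population, response will be assessed at the third week of a" participant's established iTD.
- **Any-time rule.** SAP 3.4.3: "A participant will be considered a responder if they met the" 20% threshold at any time in the DEP, counting the scheduled Week 3 visits and excluding the weekly substudy values.

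Neither 3.14.1.3 nor 3.14.1.5 calls the responder run descriptive or mentions the selection.

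**The concern.** The set is defined by the dependent variable: same baseline, same Week 3 measurements, with a cut at -20%. Even if the drug did nothing, the mean change in this set could not be expected to be zero. Adjusting for baseline Phe does not undo selection on the post-baseline value.

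The enrichment argument in Protocol 1.6.1 covers the RWP, where selection comes before randomized treatment and falls on both arms alike. The DEP is open-label and uncontrolled, so nothing offsets the selection there.

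Under the iTD rule the selected visit is always the participant's highest tolerated dose, whereas lower-dose visits are selected only through their correlation with it. That pattern alone produces a gradient across doses. It runs in the direction Protocol 1.6 expects, where a higher dose is said to lower Phe more, so a reader could take it for confirmation.

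**Working it through.** **Inputs from the documents.** Mean percent change -11%, SD 17%, 10% DEP dropout, two-sided 0.05 and about 50% responders (Protocol synopsis, Sample Size Considerations). RWP difference -245 µmol/L, SD 247, 5% dropout (same place). Response cut -20%.

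**Assumptions.** iTD mix 20/30/50% over Doses 1/2/3; correlation 0.5 between percent changes at two visits; no repeat visits after de-escalation. Enrolled N is redacted.

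**1. The plan's own power figure.** A one-sample t-test at -11%, SD 17% gives 98.1% power with 41 evaluable (46 enrolled less 10%). The stated power of over 98% fits any N of 46 or more, so it does not fix N.

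**2. A plausible N.** Per arm, n = 2(z₁₋α/₂ + z₁₋β)²(247/245)² = 16, 22 and 27 at 80, 90 and 95% power. Doubling, dividing by 0.95, then by 0.5 and 0.9, gives about 76, 105 and 127 enrolled. I used 105, with 50 and 200 as a range.

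**3. Closed form, iTD rule.** With normal change, mean m and SD 17, let a = (-20 - m)/17.
- Mean at the selected visit: m - 17·φ(a)/Φ(a).
- Mean at another visit of the same person: m + 0.5 × (selected mean - m).
- Of those with a Dose 1 visit, 20% have it as their iTD. For Dose 2 the share is 30/80 = 37.5%; for Dose 3 it is 100%.

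| | Inert, m = 0 | Flat effect, m = -11 |
|---|---|---|
| Chance of response at one visit, Φ(a) | 12.0% | 29.8% |
| Mean at the selected visit | -28.4 | -30.8 |
| Mean at another visit | -14.2 | -20.9 |
| Dose 1: 0.2 × selected + 0.8 × other | -17.0 | -22.9 |
| Dose 2: 0.375 × selected + 0.625 × other | -19.5 | -24.6 |
| Dose 3 | -28.4 | -30.8 |
| Dose 3 minus Dose 1 | -11.3 | -7.9 |

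**4. Any-time rule.** Under the same assumptions, a flat -11% shows as about -23/-22/-21.

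**5. The model itself, inert drug.** Simulated with REML, dose factor, baseline covariate, averaged duplicates and compound symmetry (the SAP's last fallback; an unstructured fit was checked at N = 200). Two degrees-of-freedom conventions bracket Kenward-Roger and give the ranges.

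| Set, enrolled N | LS means, Doses 1/2/3 (%) | All three falls significant | False dose-response (Dose 3 vs 1) significant |
|---|---|---|---|
| DEP FAS, 105 | 0/0/0 | 0% | 1.3-1.8% |
| Any-time, 50 | -18/-17/-16 | 38-67% | 0-1.6% |
| Any-time, 105 | -18/-16/-16 | 88-93% | 0.5% |
| Any-time, 200 | -18/-16/-16 | 99.8% | 0.7-1.0% |
| iTD, 50 | -16/-19/-27 | 29-73% | 5-30% |
| iTD, 105 | -16/-19/-27 | 65-88% | 25-48% |
| iTD, 200 | -16/-19/-28 | 98-99% | 67-79% |

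In the iTD row at N = 50, about half the trials had too few responders to fit, and the rates refer to the rest. A run with 20,000 enrolled gives -16/-19/-28 (iTD, gap about -12) and -17/-16/-15 (any-time). At N = 105, moving the correlation from 0.3 to 0.7 moves the iTD-rule gap from -16 to -7 points.

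**6. The model itself, flat -11%.** At 105 enrolled (about 94 completers) with the baseline covariate, the iTD rule gives -21/-23/-29, with a gap of -7.6 significant in 58-69% of trials. Without the covariate, 94 completers give 62%. The any-time rule gives -21/-21/-20 with 0.5% false dose-response. The DEP FAS run gives -11/-11/-11 with 1.0-1.5%.

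**The case against.** The strongest reply is about role. The analysis is supplementary, sits outside the DEP test sequence in SAP 3.14.1.6, and is reported beside an unselected DEP FAS run. SAP 2.1 places the primary evidence in the randomized RWP comparison, and dose dropping follows SAP Table 10 rather than this model. The SAP text for this analysis names no p-value, test against zero or dose contrast. All of that stands and limits the severity. It does not remove the bias in the estimates, and Kenward-Roger degrees of freedom serve only tests and intervals, so inference is evidently intended.

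The second reply is that a trial of an inert drug would seldom get this far. Table 10 stops for futility if fewer than 25% of DEP completers respond, and the Protocol synopsis puts the look at the first 20 completers. With a 12% chance response, 4 or fewer of 20 respond with probability about 92% under the iTD rule; under the any-time rule it is roughly 51-68%. This stands for the inert case, but not for the planned -11%, where the bias is still about 10 points or more at every dose.

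Third, a responder table does describe the DEP course of the people carried into the RWP primary analysis. That is fair, and it argues for a descriptive version rather than a model with inference.

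A reader might infer that an inert drug is bound to give a significant fall at every dose together with a false dose-response. The documents do not support that. Significance depends on the redacted N, and under the iTD rule 40 responders to an inert drug would need about 40/0.12 ≈ 335 DEP completers. The gradient arises under only one of the two responder rules; under the any-time rule the slope is slightly reversed.

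**Conclusion.** The concern holds as a bias in a supplementary analysis. In the responder RWP FAS the by-dose means overstate benefit under either responder rule: by about 15 to 28 points for an inert drug, and to roughly double or more for a flat -11%. The DEP FAS run returns the true value. A false dose-response of about -12 points (inert) or -8 points (flat -11%) appears under the iTD rule only. It would be significant in about 25-48% of inert-drug trials at an assumed 105 enrolled, and in about 60% of trials with a flat -11% effect and 94 completers.

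The direction follows from the definitions and does not depend on N. The sizes rest on the planning SD and on the assumed iTD mix and visit correlation; the significance rates also rest on N. A reader might go further and doubt the trial's efficacy conclusion. That does not follow, because the RWP contrast with placebo is made after selection, within a set common to both arms.

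**What to change.** In SAP 3.14.1.3 and 3.14.1.5, draw inference from the by-dose MMRM in the DEP FAS only. Then do one of the following:

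- delete the responder RWP FAS run; or
- keep it as descriptive summaries, without p-values, tests against zero or dose contrasts, and with a note that the set is selected on the outcome shown.

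Separately, reconcile the responder rule between SAP 2.2 (Week 3 of the iTD) and SAP 3.4.3 (any time in the DEP), since it decides who is in the set and whether the gradient appears.

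The cost is one clause in two sections, one definition to align, and the loss of a model-based responder table. If a dose-specific effect in responders is wanted, SYNB1934v1 minus placebo at RWP Week 4 within iTD level avoids this bias. It is optional and would be imprecise, because it splits a small set three ways, and comparisons across iTD levels would not be randomized.
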